**Table 8–2: PDILI laboratory measurements**

Virology-related	Hepatitis A IgM antibody
	HBsAg
	Hepatitis E IgM antibody
	HBcAb-IgM
	Hepatitis C RNA
	Cytomegalovirus IgM antibody
	Epstein-Barr viral capsid antigen IgM antibody (if unavailable, obtain heterophile antibody or monospot testing)
Immunology	Anti-nuclear antibody (qualitative and quantitative)
	Anti-smooth muscle antibody (qualitative and quantitative)
	Type 1 anti-liver kidney microsomal antibodies (qualitative and quantitative)
Hematology	Eosinophil count
Urinalysis	Toxicology screen
Chemistry	Amylase
	If total bilirubin $\geq 1.5 \times \text{ULN}$ , obtain fractionated bilirubin to obtain % direct bilirubin
	Serum CPK and LDH to evaluate possible muscle injury causing transaminase elevation
Additional	Prothrombin time/INR a
	Serum pregnancy test
	PK sample

ALT=alanine aminotransferase; CPK=creatine phosphokinase; HBcAb-IgM=hepatitis B core antibody-IgM; HBsAg=hepatitis B surface antigen; IgM=immunoglobulin M; INR=international normalized ratio; LDH=lactate dehydrogenase; PDILI=potential drug-induced liver injury; PK=pharmacokinetic; RNA=ribonucleic acid; ULN=upper limit of normal

a Measured only for subjects with ALT  $>8 \times \text{ULN}$ , elevations in total bilirubin, and symptoms of hepatitis or hypersensitivity. Hepatitis symptoms include fatigue, nausea, vomiting, and right upper quadrant pain or tenderness; hypersensitivity symptoms include eosinophilia ( $>5\%$ ), rash, and fever (without clear alternative cause).

Was revised as follows:

**Table 8–2: PDILI laboratory measurements**

Virology-related	Hepatitis A IgM antibody
	HBsAg
	Hepatitis E IgM antibody
	HBcAb-IgM
	Hepatitis C RNA
	Cytomegalovirus IgM antibody
	Epstein-Barr viral capsid antigen IgM antibody (if unavailable, obtain heterophile antibody or monospot testing)
Immunology	Anti-nuclear antibody (qualitative and quantitative)
	Anti-smooth muscle antibody (qualitative and quantitative)
	Type 1 anti-liver kidney microsomal antibodies (qualitative and quantitative)
Hematology	Hematocrit
	Hemoglobin
	Platelet count
	RBC count
	WBC count
	WBC differential count
Urinalysis	Toxicology screen
Chemistry	Amylase
	If total bilirubin $\geq 1.5 \times \text{ULN}$ , obtain fractionated bilirubin to obtain % direct bilirubin
	Serum CPK and LDH to evaluate possible muscle injury causing transaminase elevation
	ALT
	AST
	ALP
	GGT
	Albumin
Additional	Prothrombin time/INR a

	Serum pregnancy test
	PK sample

ALP=alkaline phosphatase; ALT=alanine aminotransferase; AST=aspartate aminotransferase; CPK=creatinine phosphokinase; GGT=gamma-glutamyltransferase; HBcAb-IgM=hepatitis B core antibody-IgM; HBsAg=hepatitis B surface antigen; IgM=immunoglobulin M; INR=international normalized ratio; LDH=lactate dehydrogenase; PDILI=potential drug-induced liver injury; PK=pharmacokinetic; RBC=red blood cell; RNA=ribonucleic acid; ULN=upper limit of normal; WBC=white blood cell

a Measured only for subjects with ALT >8xULN, elevations in total bilirubin, and symptoms of hepatitis or hypersensitivity. Hepatitis symptoms include fatigue, nausea, vomiting, and right upper quadrant pain or tenderness; hypersensitivity symptoms include eosinophilia (>5%), rash, and fever (without clear alternative cause).

*Clinical Study Protocol, Section 8.4.5 (Tanner Stage). New final paragraph added as follows:*

The evaluation of Tanner Stage for applicable subjects will be completed according to the tabular schedule of study procedures, [Section 16.1](#).

*Clinical Study Protocol, Section 8.4.6 (Assessment of suicidality). New second paragraph added as follows:*

Subjects enrolling directly who are  $\geq 6$  years of age will complete the “Baseline/Screening” version of the C-SSRS at Visit 1 and will complete the “Since Last Visit” version at subsequent visits. If a subject becomes 6 years of age during the study, the “Already Enrolled” version of the C-SSRS should be used at the first visit at which the subject is 6 years of age and the “Since Last Visit” version used at subsequent visits.

*Clinical Study Protocol, Section 8.4.7 (Achenbach CBCL). Original text, second, third, and fourth paragraphs:*

The same scale will be completed at the Screening Visit (subjects enrolling directly into SP848), Visit 1 (subjects enrolling from SP847 or other pediatric clinical studies in epilepsy), and Visit 13/Termination Visit (or Early Termination Visit) (all subjects) by the parent(s)/legal representative(s). The completion of the Achenbach CBCL will require approximately 45 minutes.

In both questionnaires, the occurrence of certain problems and behaviors in the past 6 months will be scored on the following scale:

- 0=not true (as far as known)
- 1=somewhat or sometimes true
- 2=very true or often true

Eight syndrome scores will be calculated from these questions, which will in turn be summarized by 2 composite scores. Additionally, for each score on the question, syndrome, and total level,

categorizations based on a normative sample will be used to evaluate normal, borderline, or clinically relevant behavior.

*Was revised as follows:*

The Achenbach CBCL will be completed according to the tabular schedule of study procedures, **Section 16.1.**

In both questionnaires, the occurrence of certain problems and behaviors (in the past 2 months for the CBCL/1½-5 version and in the past 6 months for the CBCL/6-18 version) will be scored on the following scale:

- 0=not true (as far as known)
- 1=somewhat or sometimes true
- 2=very true or often true

Syndrome scores will be calculated from these questions, which will in turn be summarized by 2 composite scores. Additionally, for each syndrome and composite scores, categorizations based on a normative sample will be used to evaluate normal, borderline, or clinically relevant behavior.

*Clinical Study Protocol, Section 8.4.8 (Bayley Scales of Infant and Toddler Development, Third Edition). Original text, final paragraph:*

The same scale will be completed at the Screening Visit (subjects enrolling directly into SP848), Visit 1 (subjects enrolling from SP847 or other pediatric clinical studies in epilepsy), and Visit 13/Termination Visit (or Early Termination Visit) (all subjects) for children from 1 month to <18 months of age enrolled in English-speaking countries.

*Was revised as follows:*

The Bayley-III scales will be completed according to the tabular schedule of study procedures, **Section 16.1.**

*Clinical Study Protocol, Section 8.4.9 (Palatability and ease of use questionnaire for LCM). New final paragraph added as follows:*

The questionnaire will be completed according to the tabular schedule of study procedures, **Section 16.1.**

*Clinical Study Protocol, Section 8.4.10 (Behavior Rating Inventory of Executive Function). Original text, fourth paragraph:*

The BRIEF rating form contains items in nonoverlapping clinical scales. These theoretically and statistically derived scales form 2 broader Indexes: Behavioral Regulation (3 scales) and Metacognition (5 scales), as well as a Global Executive Composite score.

*Was revised as follows:*

The BRIEF rating form consists of items that measure various aspects of executive functioning: Inhibit, Shift, Emotional Control, Initiate, Working Memory, Plan/Organize, Organization of materials, and Monitor. These clinical scales form 2 broader Indexes: Behavioral Regulation (3 scales) and Metacognition (5 scales), as well as a Global Executive Composite score.

*Clinical Study Protocol, Section 9.2 (Supply, handling, and storage). Original text, first paragraph:*

Lacosamide (oral solution [syrup] and tablet) is stable at room temperature and is to be stored at temperatures not exceeding 25°C (77°F). Lacosamide should not be frozen.

*Was revised as follows:*

Lacosamide (oral solution [syrup] and tablet) is stable at room temperature and is to be stored at temperatures not exceeding 25.4°C (77.7°F) or below 14.5°C (58.1°F). Lacosamide should not be frozen or refrigerated.

*Clinical Study Protocol, Section 9.5 (Alternative study treatment supply due to COVID-19 pandemic) was newly added as follows:*

When a subject can no longer return to the study site due to general circumstances but will continue in the study, the following methods may be used to provide study treatment:

- Site to subject: In instances where site staff can ship study treatment dispensed from the site pharmacy supply directly to the subject.
- Depot to subject: In instances where it is not possible for the site staff to access study treatment in the site pharmacy and/or ship study treatment dispensed from the site pharmacy supply directly to the subject.

*Clinical Study Protocol, Section 12.1.2 (Statistical analysis of safety variables). Original text, Section 12.1.2.1 and Section 12.1.2.2:*

### **12.1.2 Statistical analysis of primary variables**

The primary variables, for assessment of safety and tolerability, are AEs as well as subject withdrawals due to AEs; changes in vital signs, ECGs, clinical laboratory tests, body weight, height, and calculated BMI; and physical and neurological examination findings.

#### **12.1.2.1 AEs**

Adverse events will be coded using the Medical Dictionary for Regulatory Activities (MedDRA®), and tabulated by system organ class and preferred term.

Treatment-emergent AEs will be defined as those events which started on or after the date of first SP848 LCM administration, or whose severity worsened on or after the date of first SP848 LCM administration. Adverse events occurring within 30 days after last dose of LCM will be considered treatment emergent. The incidence of TEAEs will be presented by system organ class and preferred term. Serious AEs will also be tabulated and listed.

#### **12.1.2.2 Other safety variables**

The other safety variables include changes in laboratory parameters (ie, hematology, clinical chemistry, and urinalysis), ECG measurements, vital sign measurements (blood pressure and pulse rate), body weight, height, calculated BMI, and Tanner Stage (if applicable). The actual measurement and its change from Baseline (SP847 [or other primary study as applicable] Visit 1) or the Screening Visit (for subjects who entered directly into SP848) will be analyzed descriptively and presented by visit. In addition, shift tables may be used to evaluate the number and percentage of subjects having a different post-Baseline status when compared with their Baseline status.

The shift from Baseline to the subject's last visit at which a physical and/or neurological examination was performed post-Baseline will be summarized by category.

Laboratory, ECG, and vital signs data outside of the respective reference ranges will be listed and highlighted.

Changes in behavior and development from Baseline as measured using the Achenbach CBCL for children 18 months and older (CBCL/1½-5 and CBCL/6-18) and Bayley-III scales for children <18 months of age will be summarized descriptively and presented by visit. Changes in cognitive function as measured using the BRIEF-P/BRIEF will be summarized by descriptive statistics at each visit. Baseline is defined as Visit 1 for subjects from SP847 or other epilepsy studies. Baseline values for subjects who enroll directly into SP848 will be taken from the Screening Visit.

*Was revised as follows:*

#### **12.1.2 Statistical analysis of safety variables**

##### **12.1.2.1 Primary safety variables**

The primary variables, for assessment of safety and tolerability, are the incidence of TEAEs and the incidence of SAEs.

###### **12.1.2.1.1 AEs**

Adverse events will be coded using the Medical Dictionary for Regulatory Activities (MedDRA®), and tabulated by system organ class and preferred term.

Treatment-emergent AEs will be defined as those events which started on or after the date of first SP848 LCM administration, or whose severity worsened on or after the date of first SP848 LCM administration. Adverse events occurring within 30 days after last dose of LCM will be

considered treatment-emergent. The incidence of TEAEs will be presented by system organ class and preferred term. Serious AEs will also be tabulated and listed.

### 12.1.2.2 Other safety variables

The other safety variables include changes in laboratory parameters (ie, hematology, clinical chemistry, endocrinology, and urinalysis), 12-lead ECG measurements, vital sign measurements (blood pressure and pulse rate), physical and neurological exam findings, body weight, height, calculated BMI, and Tanner Stage (if applicable). The actual measurement and its change from Baseline (SP847 [or other primary study as applicable] Visit 1) or the Screening Visit (for subjects who entered directly into SP848) will be analyzed descriptively and presented by visit. In addition, shift tables may be used to evaluate the number and percentage of subjects having a different post-Baseline status when compared with their Baseline status.

The shift from Baseline to the subject's last visit at which a physical and/or neurological examination was performed post-Baseline will be summarized by category.

Laboratory, ECG, and vital signs data outside of the respective reference ranges will be listed and highlighted.

Changes in behavior and development from Baseline as measured using the Achenbach CBCL for children 18 months and older (CBCL/1½-5 and CBCL/6-18) and Bayley-III scales for children <18 months of age will be summarized descriptively and presented by visit. Changes in cognitive function as measured using the BRIEF-P/BRIEF will be summarized by descriptive statistics at each visit. Baseline is defined as Visit 1 for subjects from SP847 or other epilepsy studies. Baseline values for subjects who enroll directly into SP848 will be taken from the Screening Visit.

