The newer AEDs differ from older agents in several important ways, including mechanism of action, spectrum of activity, and PK characteristics (Herman and Pedley, 1998). However, more than 30% of patients have inadequate seizure control on currently-available AEDs or experience significant adverse drug effects (CHMP/EWP/566/98, 2010). Therefore, a need remains for AEDs with improved effectiveness and tolerability (Sander, 1998).

Among the newer AEDs, only 5 ( gabapentin, lamotrigine, oxcarbazepine, topiramate, and levetiracetam) have successfully demonstrated efficacy as adjunctive therapy in children with difficult to treat partial-onset seizures (Appleton et al, 1999; Duchowny et al, 1999; Elterman et al, 1999; Glauser et al, 2000; Glauser et al, 2006). Despite the availability of new AEDs, more than 25% of pediatric patients have inadequate seizure control on currently available AEDs, or experience significant adverse drug effects (Hadjiloizou and Bourgeois, 2007).

Lacosamide (LCM, Vimpat®, SPM 927, [R]-2-acetamido-N-benzyl-3-methoxypropionamide) belongs to a novel class of functionalized amino acids. It has minimal protein binding and effect on cytochrome P450 enzyme system function (reducing the risk of drug-drug interactions), high oral bioavailability, and a half-life of approximately 13 hours (in adults), which allows a twice daily (bid) dose regimen. It also displays dose-proportional PK following administration over a range of doses up to 800mg in adults.

Lacosamide has been approved as adjunctive therapy in the treatment of partial-onset seizures with or without secondary generalization in patients 16 years of age and older in the European Union (oral tablets, oral solution [syrup], and solution for intravenous [iv] infusion) and in patients 17 years of age and older in the United States (oral tablets, oral solution, and solution for iv infusion). The oral solution (syrup) is a formulation suitable for administration to children. Bioequivalence has been shown between the tablet and oral solution (syrup) formulations, comparing 2 tablets of LCM 100mg and the oral solution (syrup) containing LCM 200mg, after single-dose administration in healthy subjects. The PK of LCM and its major metabolite, SPM 12809 (O-desmethyl-LCM), in plasma, urine, and saliva were identical or very similar after single oral doses of LCM 200mg administered as tablets or as oral solution (syrup).

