During the Final Visit (2 weeks after the last LCM dose), the following will be performed:

- Concomitant medications assessment
- Concomitant AEDs assessment
- Complete physical examination
- Complete neurological examination
- 12-lead ECG (2 interpretable recordings approximately 20 to 30 minutes apart prior to vital signs assessment and collection of blood samples)
- Vital signs assessment (blood pressure and pulse)
- Body weight and height assessment
- Blood sample for clinical chemistry, hematology, and endocrinology
- Blood sample for LCM and concomitant AED plasma concentrations (at any time post-dosing with LCM)
- Urine sample for urinalysis
- Serum pregnancy test for female subjects of childbearing potential
- LCM return/compliance
- Subject diary assessment
- C-SSRS
- Adverse event reporting

*Was revised as follows:*

Subjects who complete the study or withdraw prematurely from the study, and who discontinue use of LCM (ie, taper), should complete the Final Visit 2 weeks after the final dose of study medication.

During the Final Visit, the following will be performed:

- Concomitant medications assessment
- Concomitant AEDs assessment
- Complete physical examination
- Complete neurological examination
- 12-lead ECG (2 interpretable recordings approximately 20 to 30 minutes apart prior to vital signs assessment and collection of blood samples)
- Vital signs assessment (blood pressure and pulse)

- Body weight and height assessment
- Blood sample for clinical chemistry, hematology, and endocrinology
- Urine sample for urinalysis
- Serum pregnancy test for female subjects of childbearing potential
- LCM return/compliance
- Subject diary assessment
- C-SSRS
- Adverse event reporting

*Clinical Study Protocol, Section 5.20 (Safety Follow-up telephone contact). Original text:*

The Safety Follow-Up telephone contact is required for all subjects (those who have withdrawn prematurely from the study or completed the study as planned). This telephone contact will occur 28 to 35 days after the last dose of LCM. The following should be performed via telephone:

- Concomitant medications assessment
- Concomitant AEDs assessment
- Adverse event reporting. If an AE is reported at this telephone contact, the investigator will follow the AE until a definite outcome is achieved ([Section 8.1.2](#)).

*Was revised as follows:*

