Subjects who complete the study or withdraw prematurely from the study, and who discontinue use of LCM (ie, taper), should complete the Final Visit 2 weeks after the final dose of study medication. The Final Visit is not required for subjects who participate in EP0151 or EP0152.

*Clinical Study Protocol, Section 5.20 (Safety Follow-Up telephone contact). Original text, first paragraph:*

The Safety Follow-Up telephone contact is required for all subjects (those who complete the study as planned or have withdrawn prematurely from the study). For subjects who complete the study, this telephone contact will occur 28 to 35 days after Visit 13/Termination Visit (subjects who do not undergo taper of LCM) or 28 to 35 days after the last dose of LCM (subjects who discontinue use of LCM [ie, taper]). For subjects who withdraw prematurely from the study, this telephone contact will occur 28 to 35 days after the Early Termination Visit (subjects who do not undergo taper of LCM) or 28 to 35 days after the last dose of LCM (subjects who discontinue use of LCM [ie, taper]).

*Was revised as follows:*

The Safety Follow-Up telephone contact is required for all subjects (those who complete the study as planned or have withdrawn prematurely from the study) who do not participate in EP0151 or EP0152. For subjects who complete the study, this telephone contact will occur 28 to 35 days after Visit 13/Termination Visit (subjects who do not undergo taper of LCM) or 28 to 35 days after the last dose of LCM (subjects who discontinue use of LCM [ie, taper]). For subjects who withdraw prematurely from the study, this telephone contact will occur 28 to 35 days after the Early Termination Visit (subjects who do not undergo taper of LCM) or 28 to 35 days after the last dose of LCM (subjects who discontinue use of LCM [ie, taper]). The Safety Follow-Up telephone contact is not required for subjects who participate in EP0151 or EP0152.

*Clinical Study Protocol, Section 5.21(Study conduct due to coronavirus disease 2019 pandemic) was newly added as follows:*

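### The examination shift in Section 12.1.2.2 has no on-treatment limit, so children who taper off LCM are classified two weeks off drug and pooled with children examined on drug

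*Protocol*

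**What the plan says.** Section 12.1.2.2 (Other safety variables, as revised by Amendment 8) contains three relevant provisions.

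- Its list of other safety variables includes "physical and neurological exam findings".
- For the listed variables, values and changes from Baseline "will be analyzed descriptively and presented by visit". Further shift tables are allowed but not required.
- For examinations specifically, it commits to one shift summary: "The shift from Baseline to the subject's last visit at which a physical and/or neurological examination was performed post-Baseline will be summarized by category".

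Section 5.19 (Final Visit, Amendment 8) says that subjects who complete or withdraw, and who stop LCM by taper, "should complete the Final Visit 2 weeks after the final dose of study medication". The list of assessments in that section ("During the Final Visit, the following will be performed") includes a complete physical examination and, as a separate item, "Complete neurological examination". The Year 2 schedule (Table 16-2) shows both in the Final Visit column.

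The Final Visit is not universal. Section 4.4.1.4 waives it for completers who do not taper, and Section 5.17 waives it for early withdrawals who do not taper. Section 5.19 adds: "The Final Visit is not required for subjects who participate in EP0151 or EP0152".

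Section 2 gives LCM "a half-life of approximately 13 hours (in adults"); the text at hand has no pediatric value.

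**The concern.** The purpose of an examination shift table in a long-term safety study is to show how many children developed an abnormality while taking the drug. A rule based on the last examination serves that purpose only if the last examination is on treatment. Here the schedule puts a full examination after the drug has been withdrawn, and the rule does not exclude it.

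Two consequences follow. First, for children who taper off and attend the Final Visit, an abnormality seen at the Early Termination Visit or Visit 13 is replaced by the later, drug-free result. Second, whether a child contributes an on-drug or an off-drug examination depends on whether the child stopped LCM. If stopping is related to tolerability, children with on-drug problems are over-represented among those read off drug.

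Section 2 reports central nervous system events among the most frequent TEAEs in the adult adjunctive studies, with dizziness and diplopia dose-related. Reversible neurological findings are therefore a realistic case. The same amendment ties its secondary efficacy summaries to the overall Treatment Period (Section 12.1.4.1) but sets no such limit on this safety summary.

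**Working it through.** The plan gives no figure to reproduce: this summary is descriptive, with no test, margin or power calculation. The check traces the visits and then adds two simple calculations.

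**Which examination the rule selects**

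| Child | Last scheduled examination | State |
|---|---|---|
| Tapers off and attends the Final Visit (Section 5.19) | Final Visit | 2 weeks after last dose |
| Completes and continues LCM, no taper (Section 4.4.1.4) | Visit 13 | on LCM |
| Withdraws early and continues LCM, no taper (Section 5.17) | Early Termination Visit | on LCM |
| Enters EP0151 or EP0152 (Section 5.19) | Visit 13 or Early Termination Visit | before any Final Visit |
| Should attend the Final Visit but misses it | Visit 13 or Early Termination Visit | before any off-drug examination |

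The first row is off drug and is pooled with the others. For children enrolled directly, Baseline is the Screening Visit (Section 12.1.2.2), and previous LCM use is an exclusion (Section 4.3.2, criterion 4). For a directly enrolled child in the first row, the table therefore compares a drug-free examination with another drug-free examination.

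**Is the Final Visit examination really off drug?**

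Input: half-life about 13 h (adult value, Section 2).

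- Time since last dose: 14 × 24 = 336 h.
- Half-lives elapsed: 336 / 13 = 25.8.
- Fraction remaining: 0.5^25.8 ≈ 1.7 × 10⁻⁸.

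This shows that the drug has gone. It does not show that any particular finding has resolved, so resolution needs its own term below.

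**How much the table could lose**

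Let p be the share of children with a finding at their last on-treatment examination, s the share of those children whose last examination is the Final Visit, and r the share of their findings resolved by then.

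- Shown in the table as written: p × (1 − s × r).
- Fraction of on-drug findings uncounted: s × r.

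The protocol gives none of the three. With p = 10%, s from 0.3 to 0.7 and r of 0.5 or 0.9, all assumed:

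| s | r | Uncounted (s × r) | Shown instead of 10% |
|---|---|---|---|
| 0.3 | 0.5 | 15% | 8.5% |
| 0.3 | 0.9 | 27% | 7.3% |
| 0.5 | 0.5 | 25% | 7.5% |
| 0.5 | 0.9 | 45% | 5.5% |
| 0.7 | 0.5 | 35% | 6.5% |
| 0.7 | 0.9 | 63% | 3.7% |

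The uncounted fraction does not depend on p. The formula ignores abnormalities that first appear after withdrawal, which would move the table the other way.

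**The case against.** The strongest objection is that little information is lost. Section 12.1.2.2 also presents examination findings by visit, and the Early Termination Visit has its own column in the schedule with both complete examinations. A child who stops because of a neurological effect counts as a withdrawal due to a TEAE, which is a primary safety variable (Section 4.2.1.1). TEAEs are tabulated by system organ class and preferred term and include events up to 30 days after the last dose (Section 12.1.2.1.1). This stands, and it limits the point to one descriptive summary of an other safety variable. It does not repair that summary: by-visit rows do not give one status per child, and other shift tables are optional.

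A second objection is that last-visit and on-treatment shifts answer different questions, persistence versus occurrence. That is fair, but the rule does not measure persistence off drug either, because many last examinations are on drug.

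A third is that the SAP, or the part of the protocol not at hand, may add an on-treatment table. It may. The protocol sentence still fixes the visit, and an on-treatment shift used in its place would depart from it.

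Three stronger readings are tempting, and the documents do not support them.

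- A reader might infer that every child who stops LCM is read off drug. The Final Visit is tied to taper, is waived in the cases above, and can be missed.
- A reader might infer that all on-drug findings are lost in these children. Findings that persist still show at the Final Visit; a complete loss is true only by definition, for findings that have already resolved.
- A reader might infer a bias that always favours the drug. The direction holds for reversed findings only.

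**Conclusion.** The point holds in a limited form. As written, the only examination shift to which the protocol commits uses an off-drug examination for children who taper off LCM and attend the Final Visit, classes their reversed on-drug findings as no shift, and mixes these children with others last examined on drug. That follows from the text and the schedule without any assumption.

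The size cannot be computed from the document. The 15% to 63% range rests entirely on the assumed values of s and r, and the near-absence of drug at the Final Visit rests on an adult half-life. No primary variable is affected. This is worth correcting because the table would be read as on-treatment safety, but it does not threaten the study's main safety conclusions.

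**What to change.** Replace the examination-shift sentence in Section 12.1.2.2 with text along these lines: *For physical and neurological examinations, the shift from Baseline to the last on-treatment examination (on or before the last LCM dose, including Visit 13/Termination Visit or the Early Termination Visit) will be summarized by category. Examinations at the Final Visit will be presented separately as off-treatment follow-up.* A shift to the worst on-treatment category could be added as an option.

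The cost is one sentence and one extra table. All the examinations are already scheduled, so no new visits or data are needed and no clinical rule changes. The sponsor should expect that the reported frequency of abnormal shifts may be slightly less favourable. If the SAP already defines an on-treatment shift, it is enough to align the protocol sentence with it.
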